6.8.1.1. Criteria for the Calculation of Apparent Terminal Elimination Rate Constant and Half-Life

The start of the terminal elimination phase for each patient will be defined by visual inspection and generally will be the first point at which there is no systematic deviation from the loglinear decline in concentrations.

The apparent terminal elimination rate constant (λ_z) will only be calculated when a reliable estimate can be obtained using at least 3 data points, preferably not including C_{max} , and the adjusted coefficient for determination of exponential fit (R²-adj) of the regression line is ≥ 0.7 . Parameters requiring λ_z for their calculation (eg, AUC_{0-∞}, t_{1/2}, MRT, CL and V_{ss}) will only be calculated if the R²-adj value of the regression line is ≥ 0.7 .

The following regression-related diagnostic PK parameters will be determined, when possible:

Parameter	Units	Definition
λ_z	1/h	apparent terminal elimination rate constant
λ_z Upper	h	end of exponential fit
λ_z Lower	h	start of exponential fit
$\lambda_z N$	NA	number of data points included in the log-linear regression
λ_z Span Ratio	NA	time period over which λ_z was determined as a ratio of $t_{1/2}$
R ² -adj	NA	adjusted coefficient for determination of exponential fit

Table 9 Regression-Related Diagnostic PK Parameters

Where possible, the span of time used in the determination of λ_z (ie, the difference between λ_z Upper and λ_z Lower) should be ≥ 2 half-lives. If the λ_z Span Ratio is <2, the robustness of the $t_{1/2}$ values will be discussed in the Clinical Study Report (CSR).

6.8.1.2. Criteria for the Calculation and Reporting of Area Under the Concentrationtime Curve

The minimum requirement for the calculation of AUC will be the inclusion of at least 3 consecutive concentrations above the lower limit of quantification. If there are only 3 consecutive concentrations, at least 1 should follow C_{max} .

6.8.1.3. Criteria for Handling Concentration Below the Limit of Quantification or Missing Concentration for PK Analysis

Serum concentrations below the limit of quantification (BLQ) will be assigned a value of 0 before the first measurable concentration and thereafter BLQ concentrations will be treated as missing. The following rules apply to the specific situations defined below:

- If an entire concentration-time profile is BLQ, it will be excluded from PK analysis.
- Where 2 or more consecutive concentrations are BLQ at the end of a profile, the profile will be deemed to have terminated and any further quantifiable concentrations will be set to missing for the calculation of the PK parameters, unless they are considered to be a true characteristic of the profile of the drug.
- If a predose serum concentration is missing, it will be set to 0 by default within Phoenix WinNonlin.

6.8.1.4. Treatment of Outliers in PK Analysis

If a value is considered to be anomalous due to being inconsistent with the expected PK profile, it may be appropriate to exclude the value from the PK analysis. However, the exclusion of any data must have strong justification and will be documented in the CSR.

Any quantifiable predose concentration value in the first cycle will be considered anomalous and set to missing for the PK analysis. This will be set to 0 by default in Phoenix WinNonlin.

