4.2 Intervention

Phase I

Hu3F8-BsAb is given IV over \sim 1-3 hours on Days 1 and 8 for each cycle. In cycle 1, blood is drawn for PK studies as described in Section 9.1.4.

Phase II

Hu3F8-BsAb is given IV over ~1-3 hours on Days 1 and 8 for each cycle.

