9.1.4 Pharmacokinetic (PK) studies

Blood (Table 5) will be drawn at various time points to study PK of hu3F8-BsAb. At each timepoint about 2 mL of blood will be collected for PK studies. For further details, see the laboratory manual.

Day	Time points		
1	Prior to infusion of hu3F8-BsAb infusion		
1	\sim 5 mins, 3 hrs, \sim 6-8 hrs after the end of hu3F8-BsAb infusion		
2	~24 hrs		
3	~48 hrs		
4	~72 hrs		
5	~96 hrs		
6	~120 hrs		

 Table 5
 PK schedule- Cycle 1 and Dose-Escalated Cycles

Day	Time points		
7	~144 hrs		
8	~168 hrs (prior to hu3F8-BsAb injection) If dose 2 of hu3F8-BsAb cannot be given on Day 8, a PK sample should still be drawn		
8	\sim 5 mins after the end of hu3F8-BsAb infusion dose 2		
9	~24 hrs		
10	~48 hrs		
11	~72 hrs		
12	~96 hrs		
13	~120 hrs		
14	~144 hrs		
15	~168 hrs		
Approximately 22	~336 hrs		
Approximately 28	~480 hrs		

In addition, based on our prior studies demonstrating that Cmax is highly correlative with AUC for hu3F8, patients treated both in phase I and II will undergo a single blood draw \sim 5 minutes after each hu3F8-BsAb infusion for determining Cmax for repeat dosing. We will also draw blood for Ctrough prior to the second dose of hu3F8-BsAb, prior to each hu3F8-BsAb infusion in Phase I and prior to each cycle in Phase II. Each blood draw for Cmax and Ctrough will be about 2ml. Blood for HAHA testing can be used for Ctrough prior to each cycle (see 9.3).

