6.8.2. Presentation of PK Data

If the actual time of sample collection deviates from the nominal time by more than $\pm 10\%$, the serum concentration will be flagged and may excluded from the summary statistics.

Individual concentrations deemed to be anomalous will be flagged in the listings and excluded from the summary statistics.

For PK parameters the following rule will apply:

Geometric mean and coefficient of variation will not be calculated for t_{max}.

Summary tables, arithmetic mean (+ standard deviation [SD]) figures, overlaying individual figures, and individual figures by treatment and time postdose will be provided for serum PK concentrations in the intensive PK sampling period of Phase 1. All figures will be produced on both linear-linear and linear-logarithmic scales. The +SD bars will only be displayed on the linear-linear scale. Summary tables by treatment will be provided for all PK parameters, with the exception of diagnostic regression-related PK parameters.

For sparse PK sampling in Phase 1 and 2 (prior to and \sim 5 minutes after hu3F8-BsAb infusion), serum concentrations will be listed and summarized by phase, cycle and timepoint.

7. Changes in the Conduct of the Trial or Planned Analysis

The changes indicated below are being made before any data analysis and correspond to changes to protocol version 8. None of these changes are documented as formal protocol amendments:

- MTD is not exactly defined as a maximum dose level at which ≤ 1 of 6 patients experiencing DLT but it is defined as the dose level that leads to DLT in approximately 15% of patients (posterior probability of DLT that comes closest to the toxicity level of 0.15). This has been clarified.
- A DLT Evaluable Analysis Set (defined as all patients in the dose escalation phase who receive both doses of hu3F8-BsAb in cycle 1 and had sufficient safety evaluations, or who had a DLT during the DLT evaluation period) will be considered to evaluate the toxicity instead of "all enrolled patients who received their assigned dose"
- For PFS and OS definition, first dose of treatment will be considered instead of enrollment date as defined by Tinazzi¹⁰
- Death is considered for PFS definition to be consistent with Tinazzi¹¹
- CR duration will be calculated from the time of remission (which is consistent with the definition in the statistical section of the protocol) instead of from first day of treatment (mentioned in the efficacy section of the protocol)

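### SAP 6.8.1.4 is worded so that it also catches the Day 8 pre-infusion trough in Cycle 1, and its two sentences treat that value differently; it should be limited to the sample before the first infusion on Day 1

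*SAP*

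**What the plan says.** SAP 6.8.1.4 (outliers in the PK analysis): "Any quantifiable predose concentration value in the first cycle will be considered anomalous and set to missing for the PK analysis". The next sentence adds: "This will be set to 0 by default in Phoenix WinNonlin". SAP 6.8.1.3 has a companion rule: "If a predose serum concentration is missing, it will be set to 0 by default within Phoenix WinNonlin". Neither section says which predose sample is meant.

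Protocol 4.2 gives infusions of roughly 1 to 3 hours on Days 1 and 8 of each cycle. Protocol Table 5 (section 9.1.4) schedules a Cycle 1 sample before each. The Day 8 sample is listed at "168 hrs (prior to hu3F8-BsAb injection", and the next one is taken "5 mins after the end of hu3F8-BsAb infusion dose 2". The text below the table names the Day 8 sample's purpose: "We will also draw blood for Ctrough prior to the second dose of hu3F8-BsAb".

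SAP 6.8.2 attaches a consequence to the anomalous label: "Individual concentrations deemed to be anomalous will be flagged in the listings and excluded from the summary statistics". The same section promises that pre-infusion samples from the sparse sampling will be summarised by phase, cycle and timepoint. SAP 5.2.4 keeps below-quantification (BLQ) values in summaries at LLOQ/2. SAP 6.8.1 treats Cycle 1 as one split single dose and computes AUC by the linear rule for rising and the logarithmic rule for falling concentrations.

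**The concern.** A quantifiable value before any drug has been given is anomalous. A quantifiable value seven days after an infusion is expected. The rule is framed by cycle rather than by the first infusion, so a programmer who applies it as written removes the second along with the first.

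Three things follow. First, a planned trough leaves the summary statistics when it is measurable and stays in when it is not, so a Day 8 summary would describe only the BLQ patients. Second, the 168 h point is the last one before the second infusion. Without it, the rising linear segment runs from the 144 h sample to the second peak and credits drug that was not there. Third, the two sentences of the rule lead to different AUCs, and the reader cannot tell which was produced.

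Cycle 1 of Phase I is the only profile for which SAP 6.8.1 specifies noncompartmental parameters. The PK analyses go to the DMC for its MTD and RP2D recommendation (SAP 6.7.8.2).

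**Working it through.** The documents state no AUC, trough or half-life, so there is no figure of theirs to reproduce. The check is whether the wording reaches the Day 8 sample, and what happens to AUC if it does.

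**Reach of the wording.** The Table 5 times are consistent with one continuous Cycle 1 profile: 168 h is Day 8, and 336 h and 480 h after dose 2 are Days 22 and 28. The 168 h sample lies in Cycle 1, is taken before a dose and is expected to be quantifiable when drug remains. All three conditions of the rule are met.

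**AUC: inputs from the documents.** Table 5 sampling times; infusions of 1, 2 or 3 h; linear-up/log-down AUC (SAP 6.8.1).

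**AUC: assumed inputs.** One-compartment kinetics; half-life 48, 96 or 168 h, with 24 h as an extreme; dose splits. Protocol 9.1.2.1 gives an equal split for level 1 (0.0045 per dose, 0.009 per cycle). The per-dose columns for higher levels are not visible. A small first dose of 1.3 mcg/kg is inferred from the cycle totals in SAP 6.1 (9.3 = 1.3 + 8; 21.3 = 1.3 + 20; 501.3 = 1.3 + 500) and from the priming/therapeutic distinction in SAP 6.7.1.

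**Model.** With k = ln 2 / half-life and dose D infused over T hours, the concentration at u > T hours after the start is D/(T·k)·(1 - e^(-kT))·e^(-k(u-T)). The two doses are summed. Volume cancels in the percentages.

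**One case in full** (equal unit doses, half-life 96 h, 1 h infusions). C(144) = 0.3548, C(168) = 0.2984, second peak sample at 169.083 h = 1.2919. Total AUC to the last sample = 271.28; over 0-192 h = 125.28. The segment from 144 h to the second peak is:

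- Kept: 24 × (0.3548 - 0.2984)/ln(0.3548/0.2984) + 1.083 × (0.2984 + 1.2919)/2 = 7.82 + 0.86 = 8.68.
- Missing: 25.083 × (0.3548 + 1.2919)/2 = 20.65. Excess 11.97, which is +4.4% of 271.28 and +9.6% of 125.28.
- Set to 0 (linear, since the log rule cannot take 0): 24 × 0.3548/2 + 1.083 × 1.2919/2 = 4.26 + 0.70 = 4.96. Change -3.72, which is -1.4% and -3.0%.

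**Ranges, half-life 48-168 h, all infusion times** (AUC0-8d taken as 0-192 h):

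| Day 1 / Day 8 dose | AUC0-tlast, missing | AUC0-tlast, set to 0 | AUC 0-192 h, missing | AUC 0-192 h, set to 0 |
|---|---|---|---|---|
| equal | +2.7 to +8.6% | -0.8 to -1.6% | +7.7 to +14.1% | -1.3 to -4.4% |
| 1.3 / 8 | +4.9 to +14.8% | -0.2 to -0.45% | +27 to +40% | -0.6 to -2.6% |
| 1.3 / 20 | +5.3 to +16.2% | -0.1 to -0.2% | +39 to +50% | -0.3 to -1.5% |
| 1.3 / 500 | +5.7 to +17.2% | about 0 | +53 to +61% | 0 to -0.1% |

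At a 24 h half-life, missing gives about +17% (equal) to +34% (1.3/500) for AUC0-tlast. The trough is then under 1% of the first peak and may well be BLQ. SAP 6.8.1.3 already treats a BLQ value at that point as missing, so 6.8.1.4 would add nothing.

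With the rule limited to time 0, the 168 h value is kept and the error from this source is 0.

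**The case against.** The strongest reply is that the context points to time 0. SAP 6.8.1 analyses Cycle 1 as a split single dose with intervals counted from one time zero, and section 7 repeats this. In that frame the 168 h sample is a postdose point. The sentence about defaulting to 0 fits a time-0 value and makes little sense mid-profile. SAP 6.8.1.4 also requires strong justification, documented in the study report, for any exclusion, and an ordinary Day 8 trough would offer none. The promise in 6.8.2 to summarise pre-infusion samples suggests that troughs were meant to be reported.

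This stands as evidence of intent: it makes the defect an ambiguity rather than a decision to discard troughs. It does not repair the text. Section 6.8.2 uses pre-infusion sampling for every dose, so predose is not confined to time 0 in this SAP, and the rule itself labels the value anomalous without a case-by-case judgement.

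The reply also limits three inferences a reader might draw. That the rule inflates AUC is true only if the value is left missing; under the rule's second sentence AUC falls slightly. That Cycle 1 troughs would have no summary at all is too strong: BLQ values stay in at LLOQ/2, and the listings retain every value. That the RP2D would be misjudged is not shown. PK determines it only if no DLT is observed, and may do so if the MTD is not reached. The stated criterion is highest serum levels rather than AUC, and Cmax is read directly from the profile and is unaffected.

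**Conclusion.** The wording defect is real and modest. As written, the rule covers a planned, valid sample, and following it removes quantifiable Day 8 troughs from the noncompartmental analysis and the summaries. Its effect on AUC cannot be given a single direction because the rule says two things. If the value is missing, AUC0-tlast rises by about 3-9% with equal doses and 5-17% with a small first dose, with larger effects on AUC0-8d. If it is set to 0, AUC0-tlast changes by 0 to about -1.6%. Under missing, the size depends on the dose split, so comparisons of dose-normalised AUC across levels could be distorted.

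The percentages rest on the one-compartment model and on assumed half-lives and splits. They show the order of magnitude, not a prediction for this antibody. The documents do not support a claim that the sponsor intends to drop the trough or that dose selection would change.

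**What to change.** In SAP 6.8.1.4, limit the rule to a quantifiable concentration in the sample taken before the first infusion on Cycle 1 Day 1 (time 0). Give the missing-predose bullet in 6.8.1.3 the same limit, so that a missed Day 8 sample is not entered as 0. Add one sentence stating that the Day 8 pre-infusion value at about 168 h is kept as measured, both in the noncompartmental analysis and in the summary statistics under 6.8.2.

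The cost is a few words in two SAP sections. No new samples, data or analyses are needed.

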6.8.2. Presentation of PK Data

If the actual time of sample collection deviates from the nominal time by more than $\pm 10\%$, the serum concentration will be flagged and may excluded from the summary statistics.

Individual concentrations deemed to be anomalous will be flagged in the listings and excluded from the summary statistics.

For PK parameters the following rule will apply:

Geometric mean and coefficient of variation will not be calculated for t_{max}.

Summary tables, arithmetic mean (+ standard deviation [SD]) figures, overlaying individual figures, and individual figures by treatment and time postdose will be provided for serum PK concentrations in the intensive PK sampling period of Phase 1. All figures will be produced on both linear-linear and linear-logarithmic scales. The +SD bars will only be displayed on the linear-linear scale. Summary tables by treatment will be provided for all PK parameters, with the exception of diagnostic regression-related PK parameters.

For sparse PK sampling in Phase 1 and 2 (prior to and \sim 5 minutes after hu3F8-BsAb infusion), serum concentrations will be listed and summarized by phase, cycle and timepoint.

7. Changes in the Conduct of the Trial or Planned Analysis

The changes indicated below are being made before any data analysis and correspond to changes to protocol version 8. None of these changes are documented as formal protocol amendments:

- MTD is not exactly defined as a maximum dose level at which ≤ 1 of 6 patients experiencing DLT but it is defined as the dose level that leads to DLT in approximately 15% of patients (posterior probability of DLT that comes closest to the toxicity level of 0.15). This has been clarified.
- A DLT Evaluable Analysis Set (defined as all patients in the dose escalation phase who receive both doses of hu3F8-BsAb in cycle 1 and had sufficient safety evaluations, or who had a DLT during the DLT evaluation period) will be considered to evaluate the toxicity instead of "all enrolled patients who received their assigned dose"
- For PFS and OS definition, first dose of treatment will be considered instead of enrollment date as defined by Tinazzi¹⁰
- Death is considered for PFS definition to be consistent with Tinazzi¹¹
- CR duration will be calculated from the time of remission (which is consistent with the definition in the statistical section of the protocol) instead of from first day of treatment (mentioned in the efficacy section of the protocol)
- 4-months PFS for group 2 of phase II will not be analysed using Wilson's method to provide CIs. Instead, PFS rates at 4 months using Kaplan Meier method will be displayed in order to take censoring into account. It corresponded to the exploratory analyses of the protocol. It will be now considered as the primary analysis of phase II for group 2 patients.
- ORR analyses at end of treatment excluding potential response assessments after initiation of any new prohibited anticancer treatment will be performed as sensitivity analyses
- The correlation between HAHA response and overall response rate (for neuroblastoma) or disease control rate (for osteosarcoma) will not be tested using chisquare test. Instead, logistic regression analysis with inclusion of log(therapeutic dose) as a covariate will be applied.
- Analyses about immunological effects will not be adjusted with Hochberg as they are exploratory analyses.
- Disease Control Rates will be analysed as an exploratory efficacy endpoint for phases I and II.
- Accumulation index for AUC (RA,AUC), C_{max} (RA, C_{max}) will not be calculated since the PK parameter calculation methods are based on a 'split' single dose approach.

8. Appendices

8.1. Appendix 1: Document History

Document Version, Status, Date	Summary / Reason for Changes
Version 0.1, Draft, 11Jun2021	Not applicable; the first version
Version 0.2, Draft, 06Jul2021	Sponsor comments following Draft 0.1 review
Version 1.0, Final, 06Oct2021	Sponsor comments following Draft 0.2 review

